4.6.3.2 Presentations

All laboratory data will be presented in SI or conventional units.

The haematology, chemistry and coagulation parameters defined in [Table 9](#) will be presented as continuous variables using descriptive statistics as specified in section [3.3](#) and will be presented by treatment group and by scheduled post-baseline visits for observed values and change from baseline.

The number of subjects with treatment-emergent laboratory parameter abnormalities will be presented categorically by treatment group. Only the most extreme value per subject will be accounted for.

Shift tables from baseline to maximum or minimum value will also be presented by treatment group. For INR summary table for maximum on study value as compared to baseline will be presented.

Scatter plot of maximum ALT or AST versus maximum total bilirubin and corresponding tabulation will be presented as well.

Key subject information will be presented for subjects with treatment emergent abnormalities for haematology, chemistry or coagulation abnormalities.

Additional key subject information and graphs of individual data will be presented including laboratory parameters which are associated with liver safety. This will be done for e.g. subjects with investigational product interruptions and discontinuations, subjects with DILI/modified Hy's Law.

Supportive laboratory listings will cover observed values and changes from baseline for each individual participant as well as abnormalities as compared to laboratory reference ranges.

4.6.4 Clinical Laboratory, Urinalysis

4.6.4.1 Definitions and Derivations

Safety urinalysis to be presented is the urine culture collected in the event of symptoms of urinary tract infection.

4.6.4.2 Presentations

A summary table of number and percentage of subjects with urine culture preformed and number and percentage of subjects with positive or negative urine cultures will be presented by treatment group. Percentages will be calculated with number of subjects in the analysis set as the denominator, and subjects will only be counted once per category, regardless of how many urine culture performed.

4.6.5 Other Laboratory Evaluations

Not applicable.

4.6.6 Vital Signs

4.6.6.1 Definitions and Derivations

Following Vital signs will be presented:

- Body Temperature (C)
- Body Weight (kg)
- Pulse (beats/min)
- Standing Diastolic Blood Pressure (mmHg)
- Supine Diastolic Blood Pressure (mmHg)
- Standing Systolic Blood Pressure (mmHg)
- Supine Systolic Blood Pressure (mmHg)

Treatment emergent

A treatment emergent abnormality is defined as either of below:

- A switch in parameter from normal at baseline to abnormal at post-baseline accordingly to predefined criteria, see below for predefined criteria.
- A baseline value that met the criteria for abnormality and the post-baseline value is more extreme (further from the limit), see below for predefined criteria.

Predefined criteria used for shift tables and treatment emergent reporting

The following definitions of vital sign abnormalities will be used for specified parameters:

- Body weight (kg): Low < 50, Normal \geq 50 and \leq 130, High > 130
- Body temperature (C): Low < 35, Normal \geq 35 and \leq 37.5, High > 37.5
- Supine Systolic blood pressure (mmHg): Low < 95, Normal \geq 95 and \leq 140, High > 140

- Supine Diastolic blood pressure (mmHg): Low < 60, Normal \geq 60 and \leq 100, High > 100

4.6.6.2 Presentations

Vital sign parameters will be presented for each treatment group. Vital signs for scheduled post-baseline visits will be presented descriptively for observed values and change from baseline.

Vital sign shift from baseline to maximum will be presented by treatment group.

Treatment emergent vital signs will be presented by treatment group.

Supportive vital sign listings cover observed values and changes from baseline as well as abnormalities.

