Hypotension	
The adverse clinical effect of hypotension is largely due to zibotentan's pharmacologically mediated effects of ET_A receptor antagonism resulting in vasodilation. Small reductions in systolic and diastolic blood pressure of approximately 5 mmHg has been reported with zibotentan but this has usually been asymptomatic. Dapagliflozin causes osmotic diuresis, which may lead to a small reduction in blood pressure.
	
CCI [REDACTED] according to the SoA. Participants with orthostatic hypotension or hypotension are excluded from the study (Section 5.2).
 
CCI [REDACTED] (see criteria in Section CCI [REDACTED]).
 
CCI [REDACTED] will be reported as an CCI [REDACTED] (see Section CCI [REDACTED]).

Table 2 Risk Assessment

Potential risk of clinical significance	Summary of data/rationale for risk	Mitigation strategy

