2.3.5 Overall Benefit/Risk Conclusion

The overall clinical evidence suggests that the combination of zibotentan and dapagliflozin should have clinical benefit, and an acceptable safety profile in patients with cirrhosis, justifying further drug development with appropriate risk mitigation strategies for potential risks related to hypotension, fluid retention, and heart failure.

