Alanine aminotransferase (U/L), Aspartate aminotransferase (U/L): ≥ 2 x baseline and > 1 x ULN

Direct bilirubin (mg/dL): ≥ 1 mg/dL over baseline

Total bilirubin (mg/dL): ≥ 2 x baseline and > 2 x ULN

Combination criteria: Aspartate aminotransferase (U/L) or Alanine aminotransferase (U/L) ≥ 3 x ULN and Total bilirubin (mg/dL) > 2 x ULN

Predefined criteria for Coagulation

INR: $> 0.2 +$ Baseline, $> 0.4 +$ Baseline, $> 0.6 +$ Baseline

Shift table definitions

Below parameters will be categorised according to below categories for the shift tables.

Haematology, shift from baseline to minimum value

Platelets ($10^9/L$) with categories: <50, ≥ 50 - < 75 , ≥ 75 - < 150 , ≥ 150 - < 400 , ≥ 400

Chemistry, shift from baseline to maximum value

Alanine aminotransferase (U/L), Alkaline phosphatase (U/L), Aspartate aminotransferase (U/L), Direct bilirubin (mg/dL), Total bilirubin (mg/dL) with categories: Normal(\leq ULN), High ($> 1 \times$ ULN and $\leq 2 \times$ ULN), Higher ($> 2 \times$ ULN and $\leq 5 \times$ ULN), Highest ($> 5 \times$ ULN). N-Terminal proB-type natriuretic peptide (pg/mL) with categories: Normal($\leq 1 \times 125$), High ($> 1 \times 125$ and $\leq 2 \times 125$), Higher ($> 2 \times$ ULN and $\leq 5 \times 125$), Highest ($> 5 \times 125$).

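### The only planned vital-sign shift table runs to the maximum, so it can hardly show a shift to Low blood pressure, a named risk; minor and confined to that table

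*SAP*

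**What the plan says.** SAP 4.6.6.1 sets category limits under the title "Predefined criteria used for shift tables and treatment emergent reporting". Supine systolic pressure is Low below 95 mmHg and High above 140 mmHg. Supine diastolic pressure is Low below 60 mmHg and High above 100 mmHg. Body weight and temperature also have Low and High limits.

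SAP 4.6.6.2 then gives a single direction for all of these variables: "Vital sign shift from baseline to maximum will be presented by treatment group". No shift to the minimum is planned for any vital sign. The next output is: "Treatment emergent vital signs will be presented by treatment group". The first of its two qualifying rules in 4.6.6.1 is "A switch in parameter from normal at baseline to abnormal at post-baseline accordingly to predefined criteria". The second covers a baseline already abnormal that becomes more extreme.

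The laboratory section chooses direction by parameter. For platelets the heading in SAP 4.6.3.1 is "Haematology, shift from baseline to minimum value", while liver chemistry and NT-proBNP go to the maximum.

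Protocol 2.3.5 lists "potential risks related to hypotension, fluid retention, and heart failure". Protocol Table 2 (section 2.3.3) says "Small reductions in systolic and diastolic blood pressure of approximately 5 mmHg has been reported with zibotentan", usually without symptoms, and adds that dapagliflozin may also lower blood pressure slightly.

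**The concern.** A shift table sets each participant's baseline category against the worst category reached, by arm. For blood pressure in this trial the named harm is a fall, and the table records the highest value reached. The Low category is defined for the table but can hardly be reached in it.

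A reader who turns to this table to see how many participants in each arm moved from Normal to Low would find few or none, and could mistake that for reassurance. One sentence fixes the direction for weight, temperature and blood pressure together. A maximum suits weight, where the risk is fluid retention, but it does not suit blood pressure when the question is hypotension.

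**Working it through.** The documents give no figure to reproduce on this point. The check is one of definition, followed by a rough illustration.

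**Inputs**
- Low limits: systolic below 95 mmHg, diastolic below 60 mmHg (SAP 4.6.6.1).
- Direction of shift: maximum only (SAP 4.6.6.2).
- Scheduled post-baseline readings: three after dosing at Visit 2 (60, 120 and 180 minutes) and one at each of Visits 3 to 7, so 3 + 5 = 8 (Protocol Table 1). SAP 3.3.1.1 takes the vital-sign baseline before the first dose, so the Day 1 post-dose readings are post-baseline.
- Data used for extremes: in general, all observations (SAP 3.3.2).

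**Logic**
- Maximum below 95 ⇔ all included readings below 95. One reading at or above 95 removes the participant from the Low column. The same holds for diastolic pressure at 60.
- Minimum below 95 ⇔ at least one included reading below 95.

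**Example (invented values)**
- Baseline systolic 110 (Normal). Of eight post-baseline readings, seven are 90 and one is 96.
- Maximum = 96, which is at least 95: the planned table shows Normal to Normal.
- Minimum = 90, which is below 95: a minimum shift would show Normal to Low.
- Treatment-emergent rule: baseline Normal, a later reading of 90 is Low, so this participant is counted there.

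**Illustration of size.** None of these inputs is in the documents, except that the 5 mmHg fall matches protocol Table 2. Assumed: mean systolic 110 mmHg (between-person SD 12) or 120 (SD 14); mean diastolic 70 (SD 8) or 75 (SD 9); within-person SD 6 or 10 with independent errors; eight readings; baseline at or above the Low limit; 100,000 simulated participants per scenario before the baseline restriction. At a true fall of 5 mmHg:

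| | Maximum is Low | Minimum is Low |
|---|---|---|
| Systolic | 0.3% to 1.5% | 17% to 55% |
| Diastolic | 0.5% to 2.0% | 39% to 78% |

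In a group of 22 the largest of the maximum figures is 22 × 0.020 = 0.44 participants. The minimum figures run from 22 × 0.17 = 3.7 to 22 × 0.78 = 17.2. Over falls of 0, 5 and 10 mmHg the maximum was Low in 0.06% to 9.1% of participants (at most about 2 of 22), and at least one reading was Low in 8.7% to 91%. Correlated errors, such as between the three Day 1 readings, would narrow the gap. The conclusion rests on the definition of a maximum, not on these percentages.

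**The case against.** The strongest reply is that little is lost. Protocol exclusion criterion 22 uses the same limits of 95 and 60 mmHg, and eligibility is reassessed at Visit 2, so few participants should start Low. What a minimum shift would add is then almost entirely Normal-to-Low, and the treatment-emergent table already counts that change with the same limits and by arm.

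Other outputs help too. By-visit summaries cover supine and standing pressure, and the default statistics in SAP 3.3 include the minimum. There are listings of abnormalities, adverse event tables by system organ class and preferred term, and the mixed model for supine blood pressure under key objectives 9 and 10.

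Most of this stands, and it is why the point is minor. Two things remain. None of those outputs is described as setting baseline category against lowest category by arm. And the SAP does not say that the treatment-emergent table separates Low from High. If they are pooled, falls below 95/60 mmHg are mixed with rises above 140/100 mmHg.

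A reader might infer that low blood pressure would go unseen in this trial. The documents do not support that, because the outputs just listed would show it. A reader might also infer that the data feeding the shift table are left open because 4.6.6.2 names no period. SAP 3.3.2 already points to all observations for subject-level extremes, so that is at most a matter of clearer wording.

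**Conclusion.** The point holds and is minor. The single planned vital-sign shift table runs in the wrong direction for blood pressure: a shift to Low appears only when every included reading is Low. That follows from the wording of SAP 4.6.6.1 and 4.6.6.2 alone and needs no assumption about blood pressure distributions. It is not impossible for the table to show a Low result, only unlikely.

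The consequence is one table that says little about a named risk, together with a treatment-emergent table whose wording leaves open whether Low and High are shown apart. No key endpoint, estimand or model is touched, and no blood pressure data are lost.

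**What to change.** In SAP 4.6.6.2, add a shift from baseline to minimum for supine systolic and diastolic blood pressure, and keep the shift to maximum. For the treatment-emergent vital-sign table, state that Low and High are presented separately.

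The cost is one extra table and a line of text. The data and the category limits already exist, and no key analysis changes.

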4.6.7 Electrocardiogram

4.6.7.1 Definitions and Derivations

Digital ECGs will be recorded in triplicate and the average of available observations will be used for analyses.

Following ECG parameters will be presented:

- ECG Mean Heart Rate (beats/min)
- PR Interval, Aggregate (msec)
- RR Interval, Aggregate (msec)
- QRS Duration, Aggregate (msec)
- QT Interval, Aggregate (msec)
- QTcF Interval, Aggregate (msec)

The Central ECG reading will make an assessment per ECG reading whether the ECG finding is normal or abnormal. For analyses, if multiple readings at the same visit the overall assessment will be classified as abnormal if at least one reading is abnormal. The investigator will make an overall assessment of the ECG whether the ECG finding is normal or abnormal and if abnormal, clinically significant or not. The central ECG reading will be used for summary outputs. Both central and investigator assessments will be listed.

Ranges and criteria to be used for each parameter is defined in [Table 10](#).

Table 10 Ranges and criteria for ECG presentation

Variable	Unit	Outside lower limit if	Outside upper limit if	AZ extended reference range - low	AZ extended reference range - high	Treatment emergent increase if	Extended treatment emergent increase if
Heart rate	bpm	<50	>100	<45	>120	NA	NA
				<30	>150		
RR interval	ms	<600	>1200	<500	>1333	NA	NA
				<400	>2000		
PR interval	ms	<110	>220	<100	>240	>40	>60
QRS	ms	<75	>115	<70	>120	>15	>30
QT	ms	<320	>450	<300	>480	>30	>60
					>500		
QTcF	ms	<320	>450	<300	>480	>30	>60
					>500		

ms = milliseconds, bpm = beats per minute, NA= not applicable.

Note that for treatment emergent ECGs only the increase is considered, no classification of normal/abnormal of the absolute level.

4.6.7.2 Presentations

ECG parameters will be summarised descriptively as continuous variables presented by treatment group and scheduled post-baseline visits. Observed values and change from baseline will be presented.

Overall electrocardiogram assessment (normal/abnormal) will be presented with number and percentages, by treatment group for baseline versus last observation. Overall electrocardiogram assessment (normal/abnormal) will also be presented with number and percentages, by treatment group for each scheduled timepoint.

Summary tables and key subject information presenting subjects reaching the criteria defined in [Table 10](#) for extended reference range, treatment emergent and extended treatment emergent will also be presented.

Electrocardiogram data will be listed for each participant and will include the ECG parameters (where applicable) and changes from baseline and be flagged based on lower and upper limit in [Table 10](#). Assessment by the investigator (normal/abnormal not clinically significant/abnormal clinically significant) and details of any abnormalities will be listed.

Assessment by the central reading (normal/abnormal) will also be listed together with central reading ECG findings.

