1.3 Schedule of Activities

Table 1 Schedule of Activities

	Screening period	Treatment period						Follow-up	Section in the CSP
		Randomisation	Visits						
Visit number	1	2	3	4	5	6 ^a	7		
Week	-3	0	1	2	3	6	8		
Study day	-21 to -7 ^a	1	8	15	22	43	57		
Visit window (days)			± 3	± 3	± 3	± 5	± 3		
Informed consent	X								Appendix A 3
Inclusion/exclusion criteria	X	X							Section 5.1 and Section 5.2
Alcohol breath test	X	X				X			Section 5.2
Screen for drugs of abuse	X								Section 8.3.5
AUDIT questionnaire	X								Section 8.3.6.2
Enrolment in IRT/RTSM	X								Section 6.3
Randomisation in IRT/RTSM		X							Section 6.3
Routine clinical procedures									
Demography and baseline characteristics (including smoking history and alcohol consumption)	X								Section 5.3.2

Table 1 Schedule of Activities

	Screening period	Treatment period						Follow-up	Section in the CSP
		Randomisation	Visits						
Visit number	1	2	3	4	5	6 ^a	7		
Week	-3	0	1	2	3	6	8		
Study day	-21 to -7 ^a	1	8	15	22	43	57		
Visit window (days)			± 3	± 3	± 3	± 5	± 3		
Medical/surgical history	X								
Concomitant medication	X	X	X	X	X	X	X	Section 6.9	
Body weight	X	X	X	X	X	X	X	Section 8.2.1.2	
Height, BMI calculation	X							Section 8.3.1	
ECHO	X ^c							Section 8.3.4	
HIV serology	X							Section 8.3.5	
FSH (females only)	X ^d							Section 8.3.5	
Pregnancy tests (females only; serum)	X							Section 8.3.5	
Study intervention									
Study intervention dispensed		X			X			Section 6	
Study intervention accountability (counting remaining tablets and capsules)			X	X	X	X		Section 6.2	

Table 1 Schedule of Activities

	Screening period	Treatment period						Follow-up	Section in the CSP
		Randomisation		Visits					
Visit number	1	2	3	4	5	6 ^a	7		
Week	-3	0	1	2	3	6	8		
Study day	-21 to -7 ^a	1	8	15	22	43	57		
Visit window (days)			± 3	± 3	± 3	± 5	± 3		
Study intervention intake ^a		X	X	X	X	X			Section 6
Key assessments									
Daily digital body weight measurement		Daily home measurement using a digital device should begin at Visit 2 (randomisation) to end of follow-up ^a .							Section 8.2.1.2
Bioimpedance spectroscopy ^a	X	X	X	X	X	X	X		Section 8.2.1.3
Safety assessments									
AE review ^b	X SAEs only	X	X	X	X	X	X		Section 8.4.2
Physical examination	X	X	X ^b	X ^b	X ^b	X ^b	X		Section 8.3.1
ECG central monitoring ^b	X	X (pre-dose) X (2 hours post-dose)	X	X	X	X	X		Section 8.3.3

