Follow-up Period of 2 weeks: Participants will return to the study centre for follow-up assessments approximately 2 weeks after their planned last dose of study intervention (planned last dose is at Visit 6).

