7.1 Discontinuation of Study Intervention

It may be necessary for a participant to permanently discontinue (definitive discontinuation)

study intervention.

An individual participant may be discontinued from study intervention in the following situations:

- CCI [REDACTED]; Section CCI [REDACTED].
- New diagnosis of CCI [REDACTED] of the CCI [REDACTED].
- New or worsening of symptoms of CCI [REDACTED] other than CCI [REDACTED] that is not responsive to CCI [REDACTED] doses of CCI [REDACTED].
- Overt encephalopathy (Grade 2 or higher), variceal haemorrhage, or hepatocellular cancer.
- Serious/severe CCI [REDACTED].
- Serious/severe CCI [REDACTED].
- Diabetic ketoacidosis including euglycaemic DKA have been reported with use of dapagliflozin. Consider temporary interruption of study intervention if DKA is suspected. The participant should be promptly evaluated. If DKA is confirmed, study intervention should be discontinued permanently (see Section 7.1.1 for details). If DKA is not confirmed, re-start of study intervention should be considered.
- When DILI is suspected and re-start of the study intervention is not permitted based on the algorithm outlined in Section 7.1.2.
- eGFR < 45 mL/min/1.73 m² confirmed upon repeat testing.
- Development of CCI [REDACTED] or other causes of CCI [REDACTED].
- Liver transplantation.
- Transjugular intrahepatic portosystemic shunt.
- Participant decision. The participant is at any time free to discontinue treatment, without prejudice to further treatment.
- An AE that, in the opinion of the investigator or AstraZeneca, warrants discontinuation from further dosing.
- Severe non-compliance with the CSP.
- Pregnancy: if a female participant or the female partner of a male participant becomes pregnant during the course of the study, study intervention should be discontinued immediately, and an AstraZeneca representative notified.
- Safety reasons as judged by the investigator and/or sponsor where continued treatment may put participant at undue risk.

Note that discontinuation from study intervention is NOT the same thing as a withdrawal from

the study (Section 7.2).

Participants who prematurely discontinue study intervention should remain in the study and attend all planned study visits including the Follow-up Visit as per SoA (Table 1).

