3.3.1.2 Analysis Periods

Planned treatment period

The planned treatment period starts on the date of first administration and ends on date of Visit 6.

Follow-up period

Starts the day after planned treatment period and ends on earliest of date of withdrawal of consent, death and last clinical assessment.

On-study analysis period

Starts on the date of first administration of study intervention and ends on the earliest of date of withdrawal of consent, death and last clinical assessment.

On-treatment period

Starts on the date of first administration and ends on the earliest of 28 days following the date of last dose of IMP or the end of the on-study analysis period.

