4.1.1 Subject Disposition and Completion Status

4.1.1.1 Definitions and Derivations

Disposition will be based on the Screened analysis set and following statuses are defined:

- Screened will be defined as a participant who signed ICF.
- Screen failure will be defined as a participant who signed ICF but are not subsequently randomised to a treatment group.
- Randomised will be defined as a participant who has been randomised to a treatment group.
- Randomised, not treated will be defined as a participant who has been randomised to a treatment group but who did not receive any dose of study intervention.
- Started treatment will be defined as a participant who has received at least one dose of study intervention.
- Completed treatment will be defined as a participant who has not permanently prematurely discontinued study intervention during the study.
- Discontinued treatment will be defined as a participant who have permanently prematurely discontinued study intervention.
- Completed planned treatment period will be defined as participant who has completed this period defined in section 3.3.1.2.
- Completed study will be defined as a participant who has completed all phases of the study including the follow-up visit.
- Withdraw from the study will be defined as a participant who did not complete the study.

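### The ECG normal/abnormal shift table runs to an unrestricted last observation, which on the plain reading is an ECG taken about 14 days after dosing ends

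*SAP*

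**What the plan says.** SAP 4.6.7.2 plans two summaries of the overall ECG assessment. One gives the number and percentage normal or abnormal "by treatment group for baseline versus last observation"; the other gives the same percentages at each scheduled timepoint. The term last observation is not defined, and the ECG section cites no analysis period.

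The ECG row of the schedule of activities (Protocol 1.3) covers screening, two recordings on Day 1 and every later visit. From randomisation onward the row marks the central ECG around the first dose and then at Visits 3 to 7: "X (pre-dose) X (2 hours post-dose) X X X X X" (the first cross is screening). Protocol 4.1 places follow-up after dosing has ended: "Participants will return to the study centre for follow-up assessments approximately 2 weeks after their planned last dose of study intervention", with the last planned dose at Visit 6.

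SAP 3.3.1.2 defines several periods. The on-treatment period "ends on the earliest of 28 days following the date of last dose of IMP or the end of the on-study analysis period". The planned treatment period is shorter: "The planned treatment period starts on the date of first administration and ends on date of Visit 6". For disposition, SAP 4.1.1.1 states: "Completed study will be defined as a participant who has completed all phases of the study including the follow-up visit".

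**The concern.** ECG assessments are a listed endpoint of the safety objective (Protocol Section 3, SAP Table 8). A shift table is normally the place to see how many participants moved from a normal baseline to an abnormal finding. Here the second time point falls, for most participants, after the drug has been stopped. If an abnormality arises during dosing and then resolves, that participant is counted as normal to normal.

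The other ECG summaries do not fill this gap. By-timepoint percentages do not separate new abnormalities from pre-existing ones. The baseline-linked criteria in SAP Table 10 are increases in PR, QRS, QT and QTcF; the increase columns for heart rate and RR are marked not applicable, and the SAP notes that these criteria do not use the normal/abnormal classification. A transient rhythm or morphology finding would thus be tied to its own baseline only in the individual listings.

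The choice also differs from the rest of the SAP. Laboratory shifts go to the maximum or minimum (4.6.3.2) and vital-sign shifts to the maximum (4.6.6.2).

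**Working it through.** The plan states no figure to reproduce. The check is day arithmetic on the schedule, followed by a comparison of the SAP periods.

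**1. Inputs (Protocol 1.3).** Visit 6 is Day 43 ± 5, so Days 38 to 48. Visit 7 is Day 57 ± 3, so Days 54 to 60. The planned last dose is at Visit 6.

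**2. Gap from last dose to the follow-up ECG.**
- Nominal: 57 − 43 = 14 days.
- Shortest: 54 − 48 = 6 days.
- Longest: 60 − 38 = 22 days.

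**3. Which ECG is last under each possible reading, for a participant dosed to Visit 6 with a readable Visit 7 ECG?**

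| Reading | Period closes | Visit 7 ECG |
|---|---|---|
| No limit (as written) | last ECG on file | used |
| On-study period | withdrawal of consent, death or last clinical assessment | used |
| On-treatment period | 28 days after last dose, or end of the on-study period if earlier | used, since even 22 < 28 |
| Planned treatment period | date of Visit 6 | not used |

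Only the planned treatment period excludes the follow-up ECG, and SAP 4.6.7.2 does not refer to it.

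**4. Early stoppers.** Protocol 7.1 keeps them in the visit schedule: "Participants who prematurely discontinue study intervention should remain in the study and attend all planned study visits including the Follow-up Visit". Their Visit 7 ECG is further from the last dose. Because 57 − 28 = 29, a last dose before Day 29 puts a Day 57 ECG outside the on-treatment period. It would still be the last observation under the table as written.

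**5. Illustration only.** The documents give neither a rate of new ECG abnormality nor a rate of resolution. Assume 22 participants per arm, a share p newly abnormal at Visit 6 and a share r of these normal again at Visit 7. The number abnormal on drug but shown as unshifted is 22 × p × r.
- p = 10%, r = 50%: 22 × 0.10 × 0.50 = 1.1
- p = 20%, r = 75%: 22 × 0.20 × 0.75 = 3.3
- p = 30%, r = 100%: 22 × 0.30 × 1.00 = 6.6

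Under these assumptions about 1 to 7 participants per arm would be affected. With no reversible effect the number is zero.

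**The case against.** The strongest reply is that on-drug ECG change is well covered elsewhere. SAP 4.6.7.2 itself gives normal/abnormal percentages at each scheduled timepoint, observed values and changes from baseline by visit, summaries and key subject information for the Table 10 criteria, and listings of both central and investigator assessments. Under Protocol 8.4.4, an ECG deterioration that is serious, leads to discontinuation or is judged clinically relevant is reported as an adverse event. SAP 4.6.2.2 adds a proarrhythmia table. With about 22 participants per arm, individual changes can be read from the listings. This stands: a reader might infer that on-drug abnormalities disappear from the report, and they do not. What is missing is one summarised within-participant shift.

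A reader might also infer that the active-versus-placebo contrast is biased towards no difference. The documents do not establish that. It requires a reversible drug effect on the normal/abnormal assessment, for which no rate is given. Safety data are summarised descriptively and no hypothesis is tested, so no formal decision rests on this table. Nor do the documents state its purpose; status at the end of the study is a legitimate thing to describe.

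Third, the wording does not fix the ECG for every completer. The term is undefined, a programmer could stop at Visit 6, and a missing or unreadable Visit 7 ECG would be replaced by an earlier one. That also stands, but nothing in the text directs the programmer to Visit 6.

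The treatment policy strategy in SAP 4.6 does not justify the use of Visit 7. It deals with intercurrent events such as premature discontinuation, and the scheduled end of dosing is not one. It does bear on the remedy: cutting the data at each participant's last dose would discard ECGs recorded after early discontinuation, against that strategy.

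**Conclusion.** The point holds in a limited form. As written, the only summary that links the normal/abnormal ECG assessment to the participant's own baseline uses an off-drug ECG, nominally 14 days after the last dose, for participants with a readable Visit 7 ECG. The 28-day on-treatment period would not change this for anyone dosed to Visit 6 within the visit windows. The table is therefore less informative about ECG change during dosing than the laboratory and vital-sign shift tables.

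The timing follows from the schedule and needs no assumption beyond the plain reading of last observation and a readable Visit 7 ECG. Any loss of signal is conditional on abnormalities that arise during dosing and resolve by follow-up. The size of that loss cannot be taken from the documents, and other planned outputs would still show the on-drug findings. It is worth correcting before unblinding because the correction is small.

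**What to change.** In SAP 4.6.7.2:

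1. Define the table as baseline versus last observation in the planned treatment period of SAP 3.3.1.2, which ends on the date of Visit 6. This separates follow-up from treatment and keeps ECGs recorded after early discontinuation but before Visit 6, in line with the treatment policy strategy. State also which date closes the period for a participant with no Visit 6, as 3.3.1.2 gives none.
2. Add baseline versus worst post-baseline assessment in the same period, consistent with the laboratory and vital-sign shift tables.
3. Show Visit 7 as a separate follow-up column.

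The cost is a short SAP edit and a little extra programming, with data already collected. One drawback is that the worst-value line pools several visits, and SAP 4.6.7.1 already classifies a visit as abnormal if any one reading is abnormal. Background abnormality will therefore rise in all arms, and the line should be read against placebo.
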